10.0 CRITERIA FOR EVALUATION AND ENDPOINT ANALYSIS

10.1 Complete Response

Complete Response: Negative biopsy for high grade disease at Week 25 (\pm 7 days) for the subset of patients with a CIS component at study entry, according to local pathology call. In addition, patients with a CIS component who undergo negative biopsy at Week 13 for suspicious cystoscopy and or positive cytology and have cystoscopy not suspicious for cancer and cytology not positive for malignant cells at Week 25 do not require repeat biopsy at Week 25 and will be considered to have a complete response at Week 13 and will also be counted as having a complete response at Week 25.

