7.3 Disease Assessment

See [Section 9.0](#) for disease assessment time points (approximately every 12 weeks). Disease assessment timing (cystoscopy, urine cytology, and biopsy) is to be based on calendar timing counted as weeks after registration, not based on cycles or drug administration.

Week 13:

Office cystoscopy and urine cytology will be performed 13 weeks after registration. Patients with suspicious cystoscopy or cytology findings positive for malignancy at 13 weeks (or at any other disease assessment time point) must undergo further evaluation with TURBT/biopsy, and patients with high-grade T1 or higher stage recurrences will be taken off protocol treatment. Persistent Ta or CIS at 13 weeks and low-grade recurrences at any timepoint will be tolerated without treatment interruption.

Only frankly malignant cytology (equivalent to Papanicolaou class V) will be considered "positive" and used to determine the need for bladder biopsy and further evaluation. Cytology is limited by its subjectivity and poor reproducibility so that lower grades of possible cytologic abnormalities cannot be used reliably. All patients will undergo close monitoring of the urine cytology, so that adverse changes will be noted promptly.

Week 25:

Complete response for patients with CIS component will be assessed with urine cytology, cystoscopy, and **mandatory** bladder biopsy at Week 25 (within \pm 7 days of the start of Week 25, regardless of treatment delays). If patient is found to have persistent CIS or other high-grade disease, patient will be removed from protocol treatment. Patients with CIS at study entry achieving a complete response at 25 weeks will continue on protocol therapy as planned.

CIS patients with suspicious cystoscopy findings or cytology positive for malignancy at Week 13 and a negative biopsy at Week 13 are not required to undergo the mandatory Week 25 biopsy if their Week 25 cystoscopy is not suspicious and Week 25 cytology is negative for malignancy. A patient with positive cytology but negative biopsy at Week 25

must have re-evaluation of the upper tracts via CT or MRI (including CT-IVP, CT-urogram or MR-urogram) of the abdomen and pelvis (males and females) and biopsy of the prostatic urethra (males only).

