10.4 Event

Event: Histologically proven first appearance of high-grade bladder cancer at Week 13 or later if stage \geq T1, or Week 25 or later if stage Ta or CIS, muscle-invasive bladder cancer, clinical evidence of metastatic disease, high grade upper tract urothelial carcinoma, high grade urothelial carcinoma of the prostatic urethra, or death due to any cause.

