12.0 DISCIPLINE REVIEW

12.1 Central Pathology Review

- a. All patients registered on this study will undergo central pathology review to confirm diagnosis and determine eligibility. Pathology material must be available for this purpose (see [Section 5.0](#)). The review will verify the histologic diagnosis of non-muscle invasive urothelial carcinoma of the bladder and determine the grade and pathologic stage of the tumor. Pathologic review will be conducted on an ongoing basis, but will not be verified prior to patient registration and initiation of study treatment. Similarly, all patients with CIS will undergo central review of urine cytology at 13 and 25 weeks in order to verify complete response. All bladder biopsies taken to evaluate a suspicious lesion in any patient or at the mandatory 25 week time point in patients with CIS will be reviewed centrally, but decisions to continue study treatment will be based on the local pathologist's interpretation.
- b. All pathology submissions must be entered and tracked using the SWOG online Specimen Tracking system. See [Section 15.1b](#) for information about this system.
- c. Pathology materials are to be submitted to the SWOG Biospecimen Bank (Lab #201). The Bank will scan the slides and send to the study pathologist, [REDACTED], M.D.

All specimens must be shipped at room temperature for overnight delivery, Monday through Thursday (no weekend or holiday deliveries accepted).

- d. The following materials are to be submitted for review:

Tissue

1. Three (3) representative diagnostic tumor H & E stained slides.
2. One copy of corresponding surgical pathology report.

Urine Cytology (only patients with CIS component at study entry)

1. 1 urine cytology slide (This should be the routine slide used by the site to do the cytology.)
2. Cytology report

The tissue and cytology specimens used by the study site for diagnosis must be submitted. No special specimen preparation is required. A copy of the Shipment Packing List produced by the Specimen Tracking system must be printed and placed in the pocket of the specimen bag if it has one, or in a separate resealable bag.

- e. Specimens and corresponding reports must be submitted at the following time points:

Tissue

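### Section 10.1 makes a negative Week 25 biopsy sufficient for CR and gives no effect to Week 25 cytology or to the work-up that Section 7.3 mandates when cytology is positive

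*Combined protocol and SAP*

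**What the plan says.** Section 11.3 refers to Section 10.1 for the CR endpoint. On the main route in 10.1, CR is "Negative biopsy for high grade disease at Week 25" (within 7 days either side), as read by the local pathologist. No cytology, cystoscopy or imaging condition is attached. A second route covers patients with a negative Week 13 biopsy: those who "have cystoscopy not suspicious for cancer and cytology not positive for malignant cells at Week 25 do not require repeat biopsy" are counted as CR.

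Other sections give cytology a larger part:

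- Section 7.3: "Complete response for patients with CIS component will be assessed with urine cytology, cystoscopy, and" a mandatory bladder biopsy. Positive is defined narrowly: "Only frankly malignant cytology (equivalent to Papanicolaou class V) will be considered" positive.
- Section 7.3 also foresees the discordant case: "A patient with positive cytology but negative biopsy at Week 25" "must have re-evaluation of the upper tracts via CT or MRI", and males also need a prostatic urethra biopsy. The section does not say what the result does to CR status.
- Section 12.1: "all patients with CIS will undergo central review of urine cytology at 13 and 25 weeks in order to verify complete response".
- Section 10.4 counts as EFS events, among others, "high grade upper tract urothelial carcinoma, high grade urothelial carcinoma of the prostatic urethra, or death due to any cause". Section 7.5b makes high-grade upper-tract or urethral involvement from Week 25 a reason to stop protocol treatment.
- Section 10.2 ends CR duration at the first high-grade recurrence. Section 10.5 defines recurrence as high-grade bladder cancer and names neither the upper tract nor the prostatic urethra.

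**The concern.** CR is tested first, and EFS is tested only if CR succeeds, so the classification of a few patients can decide whether the second co-primary objective is tested at all. The protocol anticipates malignant cytology with a negative biopsy, orders an investigation, and then never says whether the patient is a CR, pending or a non-responder. Because 10.1 is the operative definition and biopsy alone satisfies it, the literal answer is CR whatever the work-up shows. Any error from this source adds CRs and never removes them.

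It also affects CR duration, which 11.3 calls a key additional secondary endpoint. Taken literally, high-grade disease outside the bladder neither prevents the CR nor ends it.

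**Working it through.** **Following one patient through the text.** Take a patient with CIS at entry and, at Week 25, a negative bladder biopsy, class V cytology and high-grade upper-tract disease found by the 7.3 work-up.

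| Section | Status |
|---|---|
| 10.1 | CR |
| 10.4 | EFS event |
| 7.5b | removed from protocol treatment |
| 7.3 | as a CR, continues on treatment |
| 10.2 with 10.5 | CR duration not ended, because upper-tract disease is not named |

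For the prostatic urethra the text is less settled. Section 10.1 says biopsy, not bladder biopsy, so a high-grade prostatic urethra biopsy inside the 7-day window might be read as making the biopsy not negative. The work-up has no deadline, so it may also fall outside that window.

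**Reproducing the stated design.** Inputs from 11.3: 70 CIS patients, success at 28 or more CRs, null 30%, target 50%, continuation at the interim with 7 or more CRs in the first 25. The exact two-stage probability of success at CR probability p is

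P(p) = Σ (x = 7 to 25) C(25,x) p^x (1−p)^(25−x) × Pr[Bin(45,p) ≥ 28−x], with the last factor equal to 1 for any x of 28 or more (not reachable here).

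- P(0.30) = 0.0464 and P(0.50) = 0.9597. These match the stated 4.6% and 96%.
- Without the interim look the values are 0.0476 and 0.9639.

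**Illustrative sensitivity.** Let f be the share of all CIS patients counted as CR only because the biopsy was negative. The documents do not give f, so its values are assumptions. If the 30% null means CR free of such disease, the counted CR probability is 0.30 + f:

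| f | extra CRs (70 × f) | P(0.30 + f) |
|---|---|---|
| 0 | 0 | 4.6% |
| 1% | 0.7 | 6.7% (0.0675 to four decimals, 0.06748 to five) |
| 2% | 1.4 | 9.5% |
| 3% | 2.1 | 12.9% |
| 5% | 3.5 | 22.0% |
| 10% | 7.0 | 53.7% |

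The upper rows are demanding. At f = 3%, 3/33 = 9% of counted CRs would be false; at f = 5%, 5/35 = 14%.

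**The same question for power.** If the 50% target was instead set on the biopsy-only definition, a stricter rule lowers the counted rate to 0.50 − f. Power is then 92.2% at f = 2% (0.9225), 82.4% at 5% and 53.7% at 10%.

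**The case against.** The strongest reply is that 10.1 is a deliberate histological criterion, 7.3 only lists procedures, and 11.3 points to 10.1. No sentence in 7.3 or 12.1 says that positive cytology means non-response. Local-central agreement on CR is a separate objective (1.3a). CR concerns clearance in patients with bladder CIS, while EFS is a wider composite in which upper-tract and prostatic disease is still counted. Much of this stands, and it rules out several stronger readings that a reader might infer:

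- *That the two routes in 10.1 apply different standards.* They do not. On the second route, non-positive cytology is a condition for waiving the repeat biopsy. If cytology is positive the waiver lapses and the Week 25 biopsy decides, as on the main route.
- *That the sections flatly contradict each other on cytology.* 7.3 and 12.1 give cytology a role in CR, but neither states a classification rule for 10.1 to contradict. The defect is a missing link.
- *That every patient with positive cytology and a negative biopsy is a false CR.* The protocol sends these patients for work-up because the source is unknown. A clear work-up is compatible with CR.
- *That the true type I error is 13% to 22%.* Section 11.3 sets the 30% null for the endpoint defined in 10.1. If that null was meant on the biopsy-only definition, the error is 4.6% with no inflation. The 3% to 5% share has no source. Section 5.2g also requires upper-tract imaging within 90 days before registration and excludes prostatic urethral carcinoma within the previous 24 months, which argues for a small share.

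The reply does not explain why 12.1 reviews cytology to verify CR if cytology cannot alter it, or why the work-up has no stated consequence for the endpoint.

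**Conclusion.** The point holds as an unresolved endpoint definition. Followed literally, 10.1 gives a result that is hard to defend for a patient whose mandated work-up finds high-grade upper-tract disease, and arguably for prostatic urethral disease too. The plan does not state CR status for positive cytology with a negative biopsy, before or after the work-up.

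The size cannot be derived from the documents. The direction is known (towards success) and the stated 4.6% and 96% are correct. The rise to 6.7%, 12.9% or 22.0% rests on two assumptions: the value of f, and a null that refers to CR free of such disease. It shows that the 28/70 rule is sensitive to one to four patients; it does not estimate the actual error rate. This should be corrected because the endpoint controls the hierarchy and the repair is inexpensive.

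**What to change.** Write one classification rule, for analysis only, in 10.1:

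1. Negative biopsy and non-positive Week 25 cytology: CR.
2. Negative biopsy and positive cytology: CR only if the work-up already required by 7.3, completed within a stated window, shows no evidence of urothelial carcinoma. The criterion should not depend on grade, because imaging cannot establish it.
3. Work-up positive or missing: non-responder.

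State whether a prostatic urethra biopsy counts as a biopsy for 10.1. Reconcile 7.3, 7.5b, 10.2, 10.4, 10.5 and 12.1 with the rule, including whether high-grade disease outside the bladder ends CR duration and what effect the central cytology review has. The treatment passages in 7.3 and 7.5b need to be made consistent with each other; which should prevail is a clinical matter. Report the biopsy-only CR rate as a sensitivity analysis. Settle the rule without reference to accumulated CR results.

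Cost: revised wording, a work-up window and a missing-work-up rule. Cytology and the work-up are already required. The CR rate may be slightly lower. The sample size and the 28/70 boundary can stay if 30% and 50% refer to CR free of such disease, and the plan should say whether they do.

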10.2 Complete Response duration

Complete Response Duration: Defined as the time from date of biopsy documenting the complete response to the time of first high-grade recurrence.

10.3 Progression

Progression: Biopsy proven muscle invasive bladder cancer Stage \geq T2, nodal or distant metastasis.

10.4 Event

Event: Histologically proven first appearance of high-grade bladder cancer at Week 13 or later if stage \geq T1, or Week 25 or later if stage Ta or CIS, muscle-invasive bladder cancer, clinical evidence of metastatic disease, high grade upper tract urothelial carcinoma, high grade urothelial carcinoma of the prostatic urethra, or death due to any cause.

10.5 Recurrence

Recurrence: Histologically proven first appearance of high-grade bladder cancer at Week 13 or later if stage \geq T1, or Week 25 or later if any stage high-grade, according to local pathology call.

10.6 Progression-Free Survival

Progression-Free Survival: From time of registration to time of first documentation of progression (as defined in [Section 10.3](#)) or death due to any cause. Patients last known to be alive and not to have progressed are censored at the date of last contact.

10.7 Event-Free Survival

Event-Free Survival: From date of registration to first documentation of event (see [Section 10.4](#)). Patients last known to be alive and not to have recurred are censored at the date of last contact.

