10.10 Overall Survival

Overall Survival: From date of registration to date of death due to any cause. Patients last known to be alive are censored at the date of last contact.

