11.0 STATISTICAL CONSIDERATIONS

11.1 Patient Populations

Eligible patients are defined as registered patients who met all the pre-registration eligibility criteria listed in Section 5 that were in effect at the time of the 12/14/18 amendment. The determination of eligibility regarding Disease Related Criteria will be based on local pathology review.

Evaluable patients are defined as registered patients who received any amount of study drug (atezolizumab).

Efficacy analyses will be based on patients who are determined to be both eligible and evaluable as defined above.

Safety analyses will be based on patients who are determined to be evaluable as defined above. Patients who are registered in the study but who do not receive any study drug will not be included in safety analyses.

11.2 Estimate of Sample Size:

A sample size of 135 eligible patients (evaluable) will be enrolled over 36 months with 18 months of additional follow-up. Our goal is to enroll 70 patients with a CIS component and 65 patients with Ta or T1 disease only. One stratum may be closed prior to accrual completion to ensure adequate patient numbers in both disease groups. An additional 50% will be enrolled to account for ineligibility or initial treatment refusal resulting in a total sample size of 202. With Revision #5 (Version Date 12/14/18) a pre-registration Study Chair approval form was enacted which has significantly reduced the rate of ineligible registrations.

11.3 Analysis:

There will be two co-primary aims for this study: The first objective to be tested involves the complete response rate in the subset of patients with CIS (see [Section 10.1](#)). The second co-primary objective involves event-free survival at 18 months for all evaluable patients. A hierarchical approach will be used to test the two co-primary aims. The CIS aim will be tested first. Only if the result is statistically significant will the second primary objective be evaluated. Only patients who received at least one dose of atezolizumab per protocol will be evaluable for these two primary objectives. Both co-primary tests will be conducted at the one-sided 0.05 significance level.

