The first primary objective is the estimation of the CR rate in the subset of patients with CIS. Enrollment of 70 eligible and evaluable patients with a CIS component will be ensured. If the total number of patients out of 70 who respond is 28 (40%) or greater, the agent would be considered promising. This design has a significance level (probability of falsely declaring that an agent with a 30% complete response probability is worthy of further investigation) of 4.6%, and a power (probability of correctly declaring than an agent with a complete response rate of 50% is worthy of further investigation) of 96%. Seventy evaluable patients are sufficient to estimate the CR rate at 25 weeks (± 1 week) to within $\pm 12\%$ (95% confidence interval). Those CIS patients without a biopsy at 25 weeks will be assumed to be non-responders. Duration of CR is defined as the time from date of biopsy documenting the complete response to the time of first high-grade recurrence, and is a key additional secondary endpoint. With a CR rate of 50%, we would expect 35 patients would have a CR. We can estimate the proportion still in CR at 18 months to within $\pm 17\%$ (95% confidence interval).

One interim futility assessment will be made in the CIS subset. We will evaluate the first 25 eligible and evaluable CIS patients for pathologic response at 25 weeks. Since accrual is expected to be slow, accrual will continue while the interim evaluation is underway. A favorable evaluation would be if 7 or more CRs are seen in the first 25 eligible and evaluable CIS patients. This is equivalent to testing the alternative hypothesis of a 50% complete response rate at the one-sided $\alpha=0.02$. If results are favorable, accrual will continue to a total of 70 eligible and evaluable CIS patients.

The second primary endpoint is event-free survival (EFS) (as defined in [Section 10.0](#)) at 18 months in the mixed population of patients with either CIS or Ta or T1 disease. This objective will only be tested if the null hypothesis in the first co-primary objective is rejected as specified above. The 18-month EFS estimate will be obtained using the method of Kaplan and Meier, and the Greenwood formula will be used to estimate the variance. A 90% confidence interval will be estimated for the 18-month EFS estimate. If the lower 90% confidence bound excludes 20%, the investigators will conclude the regimen significantly improves EFS relative to historical trial data.

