Based on published rates (see table below), it is assumed that if the true 18-month EFS rate in this mixed patient population is $\leq 20\%$, then this regimen will not warrant further investigation in this setting, whereas a 30% or greater EFS rate at 18 months would be of

considerable interest. This study has a type I error rate (one-sided) of 0.05 and statistical power of 0.93.

There will be one interim analysis conducted at the end of accrual. The 99% confidence interval around the 18 month EFS Kaplan-Meier estimate will be constructed. If the upper confidence bound rules out 30% then consideration will be given to reporting the results early due to futility. There is no adjustment to the alpha for this interim test because it is based on futility. We will not consider reporting early due to efficacy. Because one of the primary endpoints occurs at 18 months and accrual is expected to be steady but modest, an interim analysis of EFS prior to this point in the trial will not be informative.

There are several trials with outcomes that can be used as historical controls for this trial. Most of these are described in [Section 2.0](#).

Drug	Study	Patients	Outcome
Valrubicin	Steinberg 2000	BCG-unresponsive CIS	21% @ 3 mo 17% @ 12 mo 8% @ 24 mo
Valrubicin	Dinney 2013	BCG-unresponsive CIS	10% @ 12 mo 3% @ 24 mo
Gemcitabine	Skinner 2013	mostly BCG unresponsive CIS/Ta/T1 (89% high grade)	28% @ 12 mo 20% @ 24 mo
Gemcitabine	DiLorenzo 2010	mix of BCG failure/unresponsive	19% @ 24 mo
Docetaxel	Lamont 2005	mix of BCG failure/unresponsive	40% @ 12 mo 25% @ 36 mo
MCNA	Morales 2015	mix of BCG failure/unresponsive	20.9% @ 12 mo (FDA analysis)
rAdIFN	Dinney 2015	BCG unresponsive CIS/Ta/T1	35% @ 1 mo

Only Valrubicin is FDA approved in this setting, and is therefore the most representative historic control. Compared to all of these studies, our intended endpoint of 30% EFS at 18 months would demonstrate a clear improvement in outcome.

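### As worded, Section 10.7 censors EFS at last contact, so a patient who stops bladder assessment but stays in contact is carried as event-free; the bias in 18-month EFS is upward or zero

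*Combined protocol and SAP*

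**What the plan says.** Section 10.7 runs EFS from registration to the first event in 10.4, and adds: "Patients last known to be alive and not to have recurred are censored at the date of last contact". Section 10.8 repeats that sentence for recurrence-free survival (RFS). Section 10.10 uses the same date for overall survival: "Patients last known to be alive are censored at the date of last contact".

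Under 10.4 a bladder event is "Histologically proven first appearance of high-grade bladder cancer at Week 13 or later if stage" T1 or higher, or from Week 25 if Ta or CIS. The list also covers muscle-invasive disease, clinical evidence of metastasis, "high grade upper tract urothelial carcinoma, high grade urothelial carcinoma of the prostatic urethra, or death due to any cause". Section 7.3 and the footnotes to 9.1 make biopsy follow from suspicious cystoscopy or positive cytology, about every 12 weeks for two years. The one mandatory biopsy on treatment is at Week 25 in CIS patients.

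Section 11.3 tests complete response (CR) in CIS patients first: "Only if the result is statistically significant will the second primary objective be evaluated". The 18-month EFS is then estimated by Kaplan-Meier with Greenwood variance: "If the lower 90% confidence bound excludes 20%, the investigators will conclude the regimen significantly improves EFS relative to historical trial data". For CR there is a missing-assessment rule: "Those CIS patients without a biopsy at 25 weeks will be assumed to be non-responders". There is none for EFS. The remark in 11.5 about methods that accommodate censoring belongs to the translational aims.

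**The concern.** For overall survival, contact settles the patient's status. For EFS it does not: a high-grade Ta, T1 or CIS recurrence can go unseen until someone looks in the bladder and takes tissue. Read literally, 10.7 keeps a patient who has stopped cystoscopy in the risk set as event-free for as long as contact lasts. A recurrence missed in that way is removed from the curve or delayed; it never adds an event. The error therefore runs in one direction.

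The trial has one arm and a fixed 20% threshold, so no concurrent group shares the error. Section 11.3 says of the threshold's source: "There are several trials with outcomes that can be used as historical controls for this trial". The documents do not show how those rates handled stopped assessment. Once the CR test has succeeded, incomplete examination can only make a positive EFS conclusion easier. It also makes the end-of-accrual futility look less likely to trigger.

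**Working it through.** **Inputs.** From 11.2 and 11.3: n = 135, null 20%, alternative 30%, one-sided 0.05, lower limit of a 90% interval, stated power 0.93. The share of patients who stop assessment and the share of missed events that surface clinically are not in the documents; both are assumed below and shown as ranges.

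**1. The plan's own figure.** The stated power reproduces with a one-sample exponential test over all follow-up. The hazards are −ln(0.20)/18 and −ln(0.30)/18, so ln(λ0/λ1) = ln(1.609/1.204) = 0.290. With about 119.7 expected events, power = Φ(√119.7 × 0.290 − 1.645) = 0.937. The decision rule in 11.3 uses only the 18-month estimate, so the checks below use that rule.

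**2. Success boundary with complete assessment.** The lower limit is p − 1.645·√(p(1−p)/135).
- 35/135: 0.2593 − 0.0620 = 0.197, which fails.
- 36/135: 0.2667 − 0.0626 = 0.204, which succeeds.

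So P(X ≥ 36 | 135, 0.20) = 0.037 and power is P(X ≥ 36 | 135, 0.30) = 0.826. The null expects 27 event-free patients.

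**3. Carried patients.** If m patients count as event-free whatever their disease status, the false-success rate is P(X ≥ 36 − m | 135 − m, 0.20).

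| m | 0 | 1 | 2 | 3 | 4 |
|---|---|---|---|---|---|
| rate | 3.7% | 5.2% | 7.0% | 9.5% | 12.5% |

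**4. Simulated stopping, last-contact rule, true EFS 20%.** Settings: 20,000 trials each; assessments every 12 weeks; stopping uniform over Weeks 13–73 with contact kept to 18 months; step-shaped and exponential curves. Ranges cover both shapes and two runs. The EFS test is simulated alone. Week 13 findings are counted at Week 25, a simplification because 10.4 counts T1 or higher from Week 13.

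| Patients stopping | All missed events surface by Week 73 | Half surface | None surface |
|---|---|---|---|
| 2% | – | 4.3–4.4% | 5.4–5.6% |
| 5% | 3.6–3.8% | 5.8–6.3% | 8.3–9.7% |
| 10% | 3.6–3.8% | 8.1–9.7% | 15.8–20.1% |

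At 5% stopping (0.05 × 135 = 6.75 patients), 0.9–1.1 patients on average are wrongly event-free with half surfacing and 1.8–2.2 with none. Mean EFS is 20.7–20.9% and 21.3–21.7%. A variant with constant hazard, stopping spread evenly over the visits and 3,000 trials per setting gives 6.4% (half hidden) to 11.7% (all hidden) at 5% stopping; another repeat gave about 5.5% to 8.7%. The size depends on the model; the direction does not.

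**5. Censoring at the last assessment, later deaths and listed events still counted.**

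| Setting | Mean EFS at true 20% | False success | Power at true 30% |
|---|---|---|---|
| Complete assessment | 20% | 3.7% | 83% |
| 5% stop, half surface | 19.7–19.8% | 3.3–3.4% | 79–80% |
| 10% stop, half surface | 19.4–19.5% | 2.7–2.8% | 76–77% |
| 5% stop, all surface | 19.4–19.5% | – | 78–79% |
| 10% stop, half surface, event-free patients twice as likely to stop | about 18.5% | – | about 68% |

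With none surfacing, the mean is 20.0% and false success 3.7–4.1%. If every stopper is truly event-free, last contact is unbiased, and last assessment gives 16.9% at 5% stopping and 12.9% at 10%.

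**The case against.** **The wording has a benign reading.** Being known alive and not recurred is a joint status, so last contact may mean the last contact at which both were known. This stands as a possibility, but the text does not say so and shares its term with overall survival. One sentence would settle it.

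**The documents make the case uncommon.** Assessments follow the calendar (7.3) and their forms are due regardless of treatment status (14.4e). Biopsy for cause is required, as is a Week 73 CT or MRI, and data coordinators pursue missing data (18.3). Under 14.4e the Follow-Up Form for off-treatment patients is due with each disease assessment before recurrence; the Follow-Up Form schedule independent of assessment (14.4m) starts only after high-grade recurrence. Routine contact and assessment therefore tend to stop together. This stands and limits frequency. Other contact remains possible, for example through treatment-cycle and late-effects forms, and none of these rules says how EFS is computed when assessment stops.

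**The CR test comes first.** A reader might infer that the trial's overall false-positive risk is 6% or more. The documents do not support that. If true CR is 30%, the CR step passes about 4.6% of the time, and a false EFS claim cannot exceed that. The figures above apply where CR is truly raised but EFS is 20%.

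**The contrast with CR is weak.** Counting missing as failure is ordinary for a binary endpoint, and 10.1 itself credits some CRs without a Week 25 biopsy. The contrast shows only that the plan considered missing assessments for one co-primary and not for the other.

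**The replacement rule has its own bias.** This stands. It cannot be called merely mildly conservative, because the loss is material if event-free patients stop more often.

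**Conclusion.** The point holds as a defect of wording with a certain direction and an unknown size. Under the literal rule in 10.7, stopped assessment biases 18-month EFS upward or not at all; with full adherence, or if every missed event surfaces by 18 months, the bias is zero. Given that the CR test is passed and true EFS is 20%, one carried patient takes the EFS test from 3.7% to 5.2%, just past its nominal 5%, and two take it to 7.0%. At an assumed 5% stopping the rate is about 6% (half of missed events surface) to 8–10% (none surface); at 2% it is about 4% to 5.6%.

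A reader might go further and conclude that the reported EFS is inflated, or that the comparison with historical rates is unfair. Neither follows: the documents give no stopping rate and do not say how the historical rates were censored. Cystectomy before Week 25 showing only Ta or CIS is also not an event under 10.4, but 5.2h requires patients to be unfit for or to refuse cystectomy, so this should be rare.

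**What to change.** In 10.7, censor patients without an event at the date of the last disease assessment (cystoscopy/cytology) showing no event. Refer to event rather than recurrence, since 10.5 covers only bladder recurrence. Make the matching change in 10.8 so that EFS and RFS agree. State whether deaths and listed events after the last assessment still count.

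Report alongside it:
- the last-contact rule, as a sensitivity analysis;
- patients without an event who lack an 18-month assessment counted as events, as a lower bound (mean EFS 19.0% and power about 71% at 5% stopping; 18.0% and 57% at 10%);
- the number of patients who stopped assessment while still in contact;
- at most, a sensitivity analysis counting cystectomy without a prior event as an event. Section 10.4 and cystectomy-free survival stay as they are.

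The cost is a text change and programming; 14.4 already collects assessment forms and cystectomy reports. Because 14.4 also holds the Revision #9 chart-lock and sign-off steps, the change should be dated before the 18-month EFS analysis. If that analysis has been run, report the last-assessment estimate beside the last-contact one.

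The statistical cost is the power loss shown above: from 83% to about 79% at 5% stopping with half surfacing, and to about 68% at 10% if event-free patients are twice as likely to stop. The new rule is unbiased only if stopping is unrelated to outcome and later events are not selectively counted, so both estimates belong in the report.
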